9.1 Study Hypotheses

Primary: Visual arts training by museum educators is associated with increased skills in cultural competency and personal reflection among nurses in clinical practice in an academic health system.

Secondary: Nurses believe training in the visual arts impacts their clinical practice and whether it can be widely applied to pedagogical nursing practice in an academic health system.

9.2 Sample Size Determination

The target sample size is 60 NYULH nurses. Sample size calculations were performed in G*Power with the following parameters

- Test statistic: Dependent samples t-test
- Effect size estimation=0.4
- Type I error probability=0.90
- Type II error probability=0.05

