2.1 Primary Objective

The main objective is to determine if a visual arts educational intervention impacts nurse cultural competency and personal reflection skills.

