9.3 Statistical Methods

Demographics will be reported with descriptive statistics including means and frequency counts.

The main objective, to determine whether visual arts training by museum educators increases nurses' skill in cultural competency and personal reflection, will be assessed with a dependent samples t-test. We will compare CAS and IRI at baseline and post-program to find if there is a significant difference in mean scores.

The secondary objective, to understand nurse beliefs about the pedagogical value of visual arts education to nursing practice, will be explored via qualitative survey (attached as separate document) and thematically analyzed.

10 Source Documents and Access to Source Data/Documents

REDCap will be the primary data collection instrument for the study.

Access to study records will be limited to IRB-approved members of the study team. The PI will permit study-related monitoring, audits, and inspections by the IRB, the sponsor, government regulatory bodies, and University compliance and quality assurance groups of all study related documents (e.g. source documents, regulatory documents, data collection instruments, study data etc.). The PI will ensure the capability for inspections of applicable study-related facilities.

Participation as an investigator in this study implies acceptance of potential inspection by government regulatory authorities and applicable University compliance and quality assurance offices.

11 Ethics/Protection of Human Subjects

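### Section 9.2 prints a Type I error of 0.90 and a Type II error of 0.05, and nowhere does the plan give a usable alpha, power or sidedness for the primary test

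*Combined protocol and SAP*

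**What the plan says.** Section 9.2 states "The target sample size is 60 NYULH nurses" and names a dependent samples t-test run in G*Power. The inputs listed are "Effect size estimation=0.4", "Type I error probability=0.90" and "Type II error probability=0.05". It does not say whether the test is one- or two-sided, and it does not define the effect size.

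No other section supplies an alpha, a power or a number of sides, and the wording on direction is mixed:

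- Section 9.1 (primary hypothesis) is directional: the training "is associated with increased skills in cultural competency and personal reflection".
- Section 2.1 is neutral: the aim is to "determine if a visual arts educational intervention impacts nurse cultural competency and personal reflection skills". Section 3.1 is neutral too.
- Section 9.3 is both. The aim is "to determine whether visual arts training by museum educators increases" the nurses' skill, but the comparison is made "to find if there is a significant difference in mean scores", with no level attached.

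Sixty is also the enrolment ceiling (Protocol Summary and section 4.6). Section 4.7.2 lets nurses skip surveys without telling anyone, and no allowance for missing second surveys is stated.

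**The concern.** A Type I error of 0.90 would declare a change in nine out of ten studies where there was none, so the line is wrong as printed. Exchanging the two labels does not repair it: a Type II error of 0.90 means 10% power. The natural guess is that alpha was 0.05 and 0.90 was the power, but the reader has to guess.

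Two things are at stake. First, the primary comparison refers to significance without a level or a sidedness. A rise in CAS or IRI with a two-sided p-value between 0.05 and 0.10 is significant one-sided at 0.05 and not significant two-sided, and nothing on record stops that choice being made after the data are seen. Second, nobody can tell what power was planned, or whether 60 is enough for it.

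**Working it through.** **Inputs.** From section 9.2: paired t-test, effect size 0.4, target n = 60, printed Type I error 0.90, printed Type II error 0.05 (power 0.95). Assumptions: 0.4 is the mean paired change divided by the SD of the changes; one score is tested without multiplicity adjustment; and n counts nurses with both surveys.

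**Formula.** The test statistic follows a noncentral t distribution with n − 1 degrees of freedom and noncentrality 0.4 × √n. One-sided power is P(T > t₁₋α). Two-sided power is P(T > t₁₋α/₂) + P(T < −t₁₋α/₂).

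**Step 1: try to reproduce 60.** The table gives the smallest n that reaches the target power.

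| Reading of section 9.2 | Two-sided | One-sided |
|---|---|---|
| As printed: alpha 0.90, power 0.95 | 9 (power 0.951) | 2 (0.955) |
| Alpha 0.05, power 0.90 | 68 (0.902) | 55 (0.900) |
| Alpha 0.05, power 0.95 | 84 | 70 |
| Alpha 0.10, power 0.95 | 70 | 55 |

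None of these gives 60. Fifty-five pairs inflated for 8% loss does (55 / 0.92 = 59.8, rounded up to 60), but the plan states no such allowance.

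**Step 2: power at 60 complete pairs, alpha 0.05.** Noncentrality is 0.4 × √60 = 3.098 on 59 degrees of freedom.

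- Two-sided: critical value 2.001, power 0.862.
- One-sided: critical value 1.671, power 0.922.

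The standardised change that 60 pairs detect with 90% power is 0.425 two-sided and 0.382 one-sided. So 60 falls a little short of 90% on one reading and exceeds it on the other.

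**Step 3: fewer complete pairs, alpha 0.05.** The protocol gives no loss rate, so 10%, 20% and 30% are assumptions.

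| Loss from 60 | Complete pairs | Two-sided | One-sided |
|---|---|---|---|
| 10% | 54 | 0.823 | 0.896 |
| 20% | 48 | 0.775 | 0.861 |
| 30% | 42 | 0.716 | 0.817 |

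Two-sided, 80% power is kept down to 52 pairs (0.808; 51 pairs give 0.7999), a loss of 8 nurses or 13%. One-sided, 90% power is kept down to 55 pairs, a loss of 5 nurses or 8%.

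**Step 4: how far the figures depend on the assumptions.** Suppose 0.4 were instead the mean change divided by the SD of the score itself. With equal SDs and pre-post correlation r, the paired effect is 0.4 / √(2(1 − r)). The plan gives no r. For assumed values of 0.3, 0.5 and 0.7 the paired effect is 0.338, 0.400 and 0.516, and power at 60 pairs is 73%, 86% and 98% two-sided, or 83%, 92% and 99% one-sided. If alpha were split equally over CAS and IRI (0.025 each, also an assumption), 60 pairs give 78.5% two-sided or 86.2% one-sided per score, with 0.4 read as the paired effect.

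**The case against.** The strongest reply is that this is an obvious slip in a small, minimal-risk study: anyone can see that alpha 0.05 and power 0.90 were meant, and 60 complete pairs exceed 80% power on either sidedness. Part of that stands. No power shortfall is shown, and the study need not be redesigned on this account. But the slip being obvious does not make the right values known. The presumed values do not return 60, no other section supplies them, and sidedness decides whether 60 is above or below 90% power.

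A second objection is that 86% and 92% are conditional: 0.4 is undefined, and two scores are tested, one of which covers four aspects of empathy. This is correct, and Step 4 shows the spread. Since the plan states no multiplicity adjustment, per-comparison power is the right figure to report, but it should be labelled as such and recomputed if the 0.4 means something else.

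A third objection is that the low enrolment reported in section 4.4 concerns recruitment, not return of the second survey, and has been answered with further invitations and workshops. That is fair: it is not evidence of loss after baseline. The freedom to skip surveys in section 4.7.2 is relevant, but the loss rates remain assumptions and the case does not rest on them.

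**Conclusion.** The concern holds and must be fixed. The two error rates in section 9.2 cannot be design values, the printed inputs lead to 9 or 2 pairs rather than 60, and the plan contains no usable alpha, power or sidedness for its primary test. At alpha 0.05, 60 complete pairs give 86% power two-sided (68 pairs needed for 90%) or 92% one-sided (55 needed). Those figures hold per comparison, unadjusted, with 0.4 as the standardised paired change. That the lines are wrong is certain; that alpha 0.05 and power 0.90 were intended is likely but needs the sponsor's confirmation. The seriousness comes from the missing decision rule, not from the size of the sample.

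**What to change.** Before the post-program surveys are analysed:

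1. Retrieve the G*Power record and check what was entered. If it cannot be found, say so in the protocol.
2. In section 9.2, replace the two error lines with the Type I error (for example 0.05), the sidedness, the definition of the 0.4, and the power of 60 complete pairs per comparison (at alpha 0.05: 86% two-sided or 92% one-sided). Recompute these if the 0.4 is not the standardised paired change or if alpha is divided between scores.
3. Repeat the same alpha and sidedness in section 9.3, and make the wording on direction in sections 2.1, 3.1, 9.1 and 9.3 agree with it.
4. Add one sentence on power at the number of completed pairs expected (for example 48 pairs: 77% two-sided or 86% one-sided).

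The cost is three or four lines of wording, small edits to align the direction, and an IRB modification under section 11.2. The stated power may look slightly less favourable. The correction does not in itself call for more participants.

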9.3 Statistical Methods

Demographics will be reported with descriptive statistics including means and frequency counts.

The main objective, to determine whether visual arts training by museum educators increases nurses' skill in cultural competency and personal reflection, will be assessed with a dependent samples t-test. We will compare CAS and IRI at baseline and post-program to find if there is a significant difference in mean scores.

The secondary objective, to understand nurse beliefs about the pedagogical value of visual arts education to nursing practice, will be explored via qualitative survey (attached as separate document) and thematically analyzed.

10 Source Documents and Access to Source Data/Documents

REDCap will be the primary data collection instrument for the study.

Access to study records will be limited to IRB-approved members of the study team. The PI will permit study-related monitoring, audits, and inspections by the IRB, the sponsor, government regulatory bodies, and University compliance and quality assurance groups of all study related documents (e.g. source documents, regulatory documents, data collection instruments, study data etc.). The PI will ensure the capability for inspections of applicable study-related facilities.

Participation as an investigator in this study implies acceptance of potential inspection by government regulatory authorities and applicable University compliance and quality assurance offices.

11 Ethics/Protection of Human Subjects

11.1 Ethical Standard

CONFIDENTIAL

This material is the property of the NYU Langone Health. Do not disclose or use except as authorized in writing by the study sponsor

Observational Study Template Version: 18 July 2022

The PI will ensure that this study is conducted in full conformity with Regulations for the Protection of Human Subjects of Research codified in 45 CFR Part 46.

11.2 Institutional Review Board

The protocol, key information sheet, informed consent form, recruitment materials, and all participant materials will be submitted to the IRB for review and approval. Approval from NYU Langone Health IRB must be obtained before any participant is enrolled. Any amendment to the protocol will require review and approval by the IRB before the changes are implemented to the study. All changes to the consent form will be IRB approved; a determination will be made regarding whether previously consented participants need to be re-consented.

MET staff will be conducting workshops as part of their paid job and will not be engaged in human subjects' research as researchers.

11.3 Informed Consent Process

11.3.1 Consent and Other Informational Documents Provided to Participants

Participants will be given information describing in detail the study intervention, study procedures, and risks prior to starting the intervention. The following consent materials are submitted with this protocol: Key Information Sheet and Informed Consent Form.

11.3.2 Consent Procedures and Documentation

Informed consent is a process that is initiated prior to the individual's agreeing to participate in the study and continues throughout the individual's study participation. The informed consent process will begin with a concise and focused presentation of the key information using an IRB-approved *Key Information Sheet*. Extensive description of risks and possible benefits of participation will be provided to potential participants. If the potential participant is still interested in participating after reading the key information form, they will continue to the consent form and select "yes" or "no" to participating in the study. Should potential participants have any questions or concerns about the study before consenting, they may contact the PI, [name], or Sub-I, [name] by phone. Phone numbers and emails for the PI and Sub-I will be provided on the REDCap e-consent form. Their participation is voluntary and confidential and neither the PI nor the Sub-I are in supervisory roles for any potential participants and are not responsible for terms of employment. The rights and welfare of the participants will be protected by emphasizing to them that their employment status, salary, or performance evaluation will not be adversely affected if they decline to participate in this study.

Following a selection of "yes" on the consent, participants will continue to the surveys. A waiver of documentation of consent will be applied for as this study is minimal risk and research procedures do not involve procedures for which written consent is normally required outside of research. In addition, this waiver would further minimize the risk of a breach of confidentiality for employees. The updated electronic consent form in REDCap will be submitted to the IRB for review in Research Navigator via Modification before use in the study. Language consistency with the IRB-approved consent materials will be reviewed and approved by the IRB before use.

11.4 Participant and Data Confidentiality

Participant emails will be the only identifiers attached to the data. Data will be stored in REDCap, only accessible to IRB-approved research staff members. Participant emails will be deleted upon completion of the study. Participant data will be kept confidential and not be accessible to anyone outside of the study team. No one on the study team is a supervisor of any participants.

CONFIDENTIAL

This material is the property of the NYU Langone Health. Do not disclose or use except as authorized in writing by the study sponsor

Data will be analyzed and reported in aggregate. At the end of the study, all records will continue to be kept in a secure location for as long a period as dictated by local IRB and Institutional regulations.

The study monitor, or representatives of the IRB may inspect all documents and records required to be maintained by the investigator.

11.5 Future Use of Stored Data

Data collected as part of this study will not be stored for future research.

12 Data Handling and Record Keeping

12.1 Data Collection and Management Responsibilities

Data collection is the responsibility of the study staff at the site under the supervision of the PI. The investigator is responsible for ensuring the accuracy, completeness, legibility, and timeliness of the data reported. All data will be collected and stored in REDCap, accessed exclusively by research staff.

12.2 Study Records Retention

Study documents and data will be retained for the longer of 3 years after close out or 5 years after final reporting/publication. These documents should be retained for a longer period, however, if required by local regulations. No records will be destroyed without the written consent of the sponsor, if applicable. It is the responsibility of the sponsor to inform the investigator when these documents no longer need to be retained.

12.3 Protocol Deviations

A protocol deviation is any noncompliance with the study protocol or MOP requirements. The noncompliance may be either on the part of the participant, the investigator, or the study site staff. As a result of deviations, corrective actions are to be developed by the site and implemented promptly.

It is the responsibility of the site to use continuous vigilance to identify and report deviations within 5 working days of identification of the protocol deviation, or within 5 working days of the scheduled protocol-required activity. All deviations must be addressed in study source documents, reported to the IRB. Protocol deviations must be reported to the local IRB per their guidelines. The site PI/study staff is responsible for knowing and adhering to their IRB requirements. Further details about the handling of protocol deviations will be included in the MOP.

12.4 Publication and Data Sharing Policy

N/A

13 Study Finances

13.1 Funding Source

CONFIDENTIAL

This material is the property of the NYU Langone Health. Do not disclose or use except as authorized in writing by the study sponsor

Observational Study Template Version: 18 July 2022

National Network of the Library of Medicine
National Library of Medicine, NIH

13.2 Costs to the Participant

There will be no costs to participants.

13.3 Participant Reimbursements or Payments

Each participant will receive a travel stipend of \$50, complimentary entry to the museum to participate in the class, plus an additional complimentary ticket to be used at any other time that you wish. Participants will also be provided with a bag of art supplies for them to keep. Screen shots of selected art supplies will be attached in research navigator.

14 Conflict of Interest Policy

The independence of this study from any actual or perceived influence, such as by the pharmaceutical industry, is critical. Therefore any actual conflict of interest of persons who have a role in the design, conduct, analysis, publication, or any aspect of this study will be disclosed and managed. Furthermore, persons who have a perceived conflict of interest will be required to have such conflicts managed in a way that is appropriate to their participation in the study. The study leadership has established policies and procedures for all study group members to disclose all conflicts of interest and will establish a mechanism for the management of all reported dualities of interest.

Any investigator who has a conflict of interest with this study (patent ownership, royalties, or financial gain greater than the minimum allowable by their institution, etc.) must have the conflict reviewed by the NYU Langone Conflict of Interest Committee with a Committee-sanctioned conflict management plan that has been reviewed and approved by the study sponsor prior to participation in this study. All NYULH investigators will follow the applicable conflict of interest policies.

CONFIDENTIAL

This material is the property of the NYU Langone Health. Do not disclose or use except as authorized in writing by the study sponsor

Observational Study Template Version: 18 July 2022

15 References

Aoki, Y., & Katayama, H. (2021). Development of the Clinical Interpersonal Reactivity Index to evaluate nurses' empathy. *Nursing & health sciences*, 23(4), 862–870. <https://doi.org/10.1111/nhs.12875>

